# 12.4.4 Overall Response Assessment

# Table 5: Overall Response Evaluation for Neuroblastoma Patients and MIBG Positive Disease Only

If patients are enrolled without disease measurable by CT/MRI, any new or newly identified lesion by CT/MRI that occurs during therapy would be considered progressive disease.

MIBG	CT/MRI	Bone Scan	Bone Marrow	Catechol	Overall
PD	Any	Any	Any	Any	PD
Any	New Lesion	Any	Any	Any	PD
Any	Any	PD	Any	Any	PD
Any	Any	Any	PD	Any	PD
SD	No New Lesion	Non-PD	Non-PD	Any	SD
PR	No New Lesion	Non-PD	Non-PD	Any	PR
CR	No New Lesion	Non-PD	Non-PD	Elevated	PR
CR	No New Lesion	CR	CR	Normal	CR

THIS PROTOCOL IS FOR RESEARCH PURPOSES ONLY, SEE PAGE 1 FOR USAGE POLICY

ADVL1515

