#### 5.2 Criteria for Starting Subsequent Cycles

A cycle may be repeated every 28 days if the patient has at least stable disease and has again met laboratory parameters as defined in the eligibility section, Section 4.0.

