# 12.2.2 Disease Parameters

- 12.2.2.1 Measurable disease: Measurable lesions are defined as those that can be accurately measured in at least one dimension (longest diameter to be recorded) as  $\geq 20$  mm by chest x-ray, as  $\geq 10$  mm with CT scan, or  $\geq 10$  mm with calipers by clinical exam. All tumor measurements must be recorded in millimeters (or decimal fractions of centimeters).
  - Note: Tumor lesions that are situated in a previously irradiated area must show definitive evidence of progression to be considered measurable.
- 12.2.2.2 Malignant lymph nodes: To be considered pathologically enlarged and measurable, a lymph node must be  $\geq$  15 mm in short axis when assessed

institute of the National Institutes of Health

THIS PROTOCOL IS FOR RESEARCH PURPOSES ONLY, SEE PAGE 1 FOR USAGE POLICY

by CT scan (CT scan slice thickness no greater than 5 mm). At baseline and in follow-up, only the short axis will be measured and followed.

- 12.2.2.3 Non-measurable disease: All other lesions (or sites of disease), including small lesions (longest diameter < 10 mm or pathological lymph nodes with  $\geq 10$  to < 15 mm short axis), are considered non-measurable disease. Bone lesions, leptomeningeal disease, ascites, pleural/pericardial effusions, lymphangitis cutis/pulmonitis, inflammatory breast disease, and abdominal masses (not followed by CT or MRI), are considered as non-measurable.
  - Note: Cystic lesions that meet the criteria for radiographically defined simple cysts should not be considered as malignant lesions (neither measurable nor non-measurable) since they are, by definition, simple cysts. 'Cystic lesions' thought to represent cystic metastases can be considered as measurable lesions, if they meet the definition of measurability described above. However, if non-cystic lesions are present in the same patient, these are preferred for selection as target lesions.

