# 12.2.4 Response Criteria for Patients with Solid Tumor and Measurable Disease

# 12.2.4.1 Evaluation of Target Lesions

Complete Response (CR) :	Disappearance of all target and non-target lesions. Any pathological lymph nodes (whether target or non-target) must have reduction in short axis to <10 mm. If immunocytology is available, no disease must be detected by that methodology. Normalization of urinary catecholamines or other tumor markers if elevated at study enrollment (for patients with neuroblastoma).
Partial Response (PR):	At least a 30% decrease in the sum of the diameters of target lesions, taking as reference the baseline sum diameters
Progressive Disease (PD) :	At least a 20% increase in the sum of the diameters of target lesions, taking as reference the smallest sum on study (this includes the baseline sum if that is the smallest on study). In addition to the relative increase of 20%, the sum must also demonstrate an absolute increase of at least 5 mm. (Note: the appearance of one or more new lesions is also considered progressions). Note: in presence of SD or PR in target disease but unequivocal progression in non-target or non-measurable disease, the patient has PD if there is an overall level of substantial worsening in non-target disease such that the overall tumor burden has increased sufficiently to merit discontinuation of therapy

Institute of the National Institutes of Health

Stable Disease (SD):

Neither sufficient shrinkage to qualify for PR nor sufficient increase to qualify for PD, taking as reference the smallest sum diameters while on study

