- 1. Complete response: all areas of uptake on MIBG scan completely resolved. If morphological evidence of tumor cells in bone marrow biopsy or aspiration is present at enrollment, no tumor cells can be detected by routine morphology on two subsequent bilateral bone marrow aspirates and biopsies done at least 21 days apart to be considered a Complete Response.
- 2. **Partial response**: Relative score  $\leq 0.2$  (lesions almost disappeared) to  $\leq 0.5$ (lesions strongly reduced).
- 3. Stable disease: Relative score > 0.5 (lesions weakly but significantly reduced) to 1.0 (lesions not reduced).
- 4. Progressive disease: New lesions on MIBG scan.

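### Table 5 for MIBG-positive neuroblastoma has no CT/MRI entry for progression of an existing non-measurable lesion, and so conflicts with the protocol's other response rules

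*Combined protocol and SAP*

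**What the plan says.** Table 5 is titled "Overall Response Evaluation for Neuroblastoma Patients and MIBG Positive Disease Only". Its lead-in defines the population and the CT/MRI rule together: "If patients are enrolled without disease measurable by CT/MRI", then "any new or newly identified lesion by CT/MRI that occurs during therapy would be considered progressive disease". The CT/MRI column has three entries: *Any*, *New Lesion* and *No New Lesion*. Only *New Lesion* leads to PD, and every SD, PR and CR row carries *No New Lesion*.

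Having no measurable disease is not the same as having no visible lesion. Section 12.2.2.3 classes as non-measurable all remaining lesions, "including small lesions (longest diameter < 10 mm or pathological lymph nodes with" a short axis of at least 10 but under 15 mm. It adds further sites, beginning "Bone lesions, leptomeningeal disease, ascites, pleural/pericardial effusions". Section 12.2.2.5 requires lesions that are not targets to be identified and recorded at baseline.

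Other sections also bear on these lesions:

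- 12.2.1.2 assesses non-measurable lesions by presence, absence or unequivocal progression.
- 12.2.4.2 makes unequivocal progression of existing non-target lesions PD, with a condition on what counts as unequivocal.
- Table 2 of 12.2.5, for non-measurable disease, gives overall PD for unequivocal progression whether or not there is a new lesion.
- 12.3.5 counts radiographic progression as PD in evaluable disease.
- The neuroblastoma table that closes 12.2.5 has a row in which CT/MRI PD gives overall PD.

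Section 12.4.4 refers to none of these.

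**The concern.** A patient who fits Table 5's lead-in and has a recorded non-measurable CT/MRI lesion can show unequivocal progression of that disease without any new lesion. Table 5 has no place for this finding, so the patient falls under *No New Lesion*. The same patient is PD under the general rules. Two assessors could reach different overall responses, each with support in the text.

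Best response is built from these overall assessments (12.4.5 and 12.7). It feeds secondary aim 1.2.1, preliminary antitumor activity, in a tumor type that the background section describes as sensitive to CHK1 inhibition. The discrepancy runs one way: read alone, Table 5 can only give a better response than the general rules.

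**Working it through.** The plan gives no figure to reproduce. The check applies Table 5 as written and compares the result with the other sections.

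**Step 1: can another column catch the progression?** On central review, MIBG PD is "New lesions on MIBG scan", so growth of an existing lesion does not trigger it. The Bone Scan and Bone Marrow columns each have a PD row and may catch growth of a bone lesion. The gap is therefore mainly small soft-tissue lesions and nodes of 10 to under 15 mm, plus any bone growth that the bone scan does not call PD.

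**Step 2: what does Table 5 return?** Assume progression of an existing non-measurable CT/MRI lesion, no new lesion, and no PD in another column. The inputs are the eight rows of Table 5. The free states are MIBG (SD, PR, CR), bone scan (CR, or neither CR nor PD), marrow (the same two) and catecholamines (elevated, normal): 3 × 2 × 2 × 2 = 24 combinations.

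| MIBG | Catecholamines | Combinations | Overall by Table 5 |
|---|---|---|---|
| SD | any | 8 | SD |
| PR | any | 8 | PR |
| CR | elevated | 4 | PR |
| CR | normal, bone scan and marrow both CR | 1 | CR |
| CR | normal, bone scan or marrow not CR | 3 | no row applies |

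Totals: PD 0, SD 8, PR 8 + 4 = 12, CR 1, unmatched 3; 0 + 8 + 12 + 1 + 3 = 24. These count table cells. They do not show how often each occurs.

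**Step 3: what do the other sections return?** If the progression is unequivocal in the sense of 12.2.4.2, that section and Table 2 give PD. Section 12.3.5 gives PD for radiographic progression. Section 12.2.1.2 names unequivocal progression as one of the things the assessment rests on. The companion neuroblastoma table shows that a CT/MRI PD entry fits this format.

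**Step 4: what follows for the reported result?** By Table 3 of 12.7.1, two stable assessments give stable disease and two PRs give PR, but either first result followed by progression gives progressive disease. A different reading at the second assessment therefore changes best response. Under 12.7.2 it also extends the duration of response or of stable disease, which runs until progression.

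**Step 5: size.** The number of neuroblastoma patients is not given. Section 11.1 expects at most 36 enrolled, with an absolute maximum of 65. With all enrolled patients as the denominator (an assumption), one PR that should be PD moves the response proportion by 1/36 = 2.8 percentage points, or 1/65 = 1.5 points. A smaller, response-evaluable denominator would make the shift larger.

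**The case against.** The strongest reply is that Table 5 was not written for these patients. Its title can be read as limiting it to disease seen on MIBG alone. For such patients a new or newly identified lesion is the only CT/MRI event possible, and the table is complete. That reading is open, but the lead-in speaks of measurable disease and does not exclude visible non-measurable lesions. The text does not settle the scope.

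A second reply is that Table 5 is not the only rule. This stands in part. A reader might infer that such progression must be scored SD or PR, and the documents do not support that: 12.2.1.2, 12.2.4.2, Table 2 and 12.3.5 remain in force, and nothing says that Table 5 overrides them. Equally, nothing says that they override Table 5, which is the only table combining MIBG with CT/MRI for patients without measurable disease.

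Three further inferences go too far:

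- *Any obvious growth is PD under the general rules.* Section 12.2.4.2 requires a change in the disease as a whole and excludes an isolated increase in one lesion. A single lesion going from 9 mm to 27 mm with unchanged MIBG is thus not automatically PD. Nor does the note in 12.2.4.1, "unequivocal progression in non-target or non-measurable disease, the patient has PD", settle it: the note presupposes target disease, which these patients lack, and adds a condition on overall tumor burden.
- *A misread response goes unexamined for two or three cycles.* After a first PR or CR, footnote 5 of the Section 8.1 table calls for evaluation at the next consecutive cycle, and 8.2 sends responders to central review.
- *Table 5 keeps patients on treatment.* Section 5.2 says "A cycle may be repeated every 28 days if the patient has at least stable disease", so an SD reading could support another cycle. But 10.1(a) provides for removal on clinical or radiographic progression and refers to all of Section 12.0, so continuation is possible but not implied.

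**Conclusion.** The concern holds as an omission in Table 5 and an unresolved conflict with 12.2.1.2, 12.2.4.2, Table 2 of 12.2.5 and 12.3.5. It also differs from the companion neuroblastoma table. For unequivocal progression of recorded non-measurable CT/MRI disease with no PD elsewhere, Table 5 alone never returns PD.

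This rests on two assumptions: that the lead-in, rather than the narrower reading of the title, sets the table's scope, and that the progression meets the condition in 12.2.4.2.

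The consequence is modest. It touches best response and duration for an unknown, probably small, number of patients. Section 11.5 makes the response analysis descriptive and exploratory. The DLT, MTD and dose-escalation rules do not depend on it. The change is still worth making, because a stated table contradicts other stated rules, always towards a better reported response.

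**What to change.** Reconcile Table 5 with the other sections for response classification:

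- Change *New Lesion* in the CT/MRI column to *New lesion, or unequivocal progression of existing non-measurable disease as defined in 12.2.4.2*.
- Change *No New Lesion* to *Non-PD*.
- Extend the lead-in sentence in the same way.

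Citing 12.2.4.2 keeps its safeguard against calling PD on one enlarged lesion. If the table is meant only for patients with no CT/MRI lesion at all, the lead-in should say so and name the section that governs the others.

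The same edit could settle two neighboring points that this wording leaves open: the three combinations in Step 2 that match no row, and whether a persisting, unchanged non-measurable CT/MRI lesion is compatible with the CR row.

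The cost is wording in one column and one sentence, with no added scans. Slightly fewer patients would be reported as SD or PR.

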#### 12.4.5 Overall Best Response Assessment

Each patient will be classified according to his "best response" for the purposes of analysis of treatment effect. Best response is determined from the sequence of the overall response assessments as described in Table 3 in Section 12.7.

#### 12.5 **Response Criteria for Neuroblastoma Patients with Bone Marrow Involvement**

#### 12.5.1 Bone Marrow Involvement

Bone marrow obtained within 14 days prior to study enrollment with tumor cells seen on routine morphology (not by immunohistochemical staining only) of bilateral aspirate or biopsy on one bone marrow sample.

Bone Marrow responses are determined by H&E Staining of bilateral bone marrow biopsies and aspirates.

Complete Response:	No tumor cells detectable by routine morphology on 2
	consecutive bilateral bone marrow aspirates and biopsies
	performed at least 21 days apart. Normalization of urinary
	catecholamines or other tumor markers if elevated at
	study enrollment.

**Progressive Disease:** In patients who enroll with neuroblastoma in bone marrow by morphology have progressive disease if there is a doubling in the amount of tumor in the marrow AND a minimum of 25% tumor in bone marrow by morphology. (For example, a patient entering with 5% tumor in marrow by morphology must increase to  $\geq 25\%$ tumor to have progressive disease; a patient entering with 30% tumor must increase to > 60%).

> In patients who enroll without evidence of neuroblastoma in bone marrow will be defined as progressive disease if tumor is detected in 2 consecutive bone marrow biopsies or aspirations done at least 21 days apart.

Stable Disease: Persistence of tumor in bone marrow that does not meet the criteria for either complete response or progressive disease.

## 12.5.2 Overall Best Response Assessment

Each patient will be classified according to his "best response" for the purposes of analysis of treatment effect. Best response is determined from the sequence of the overall response assessments as described in Section 12.7.

#### 12.6 **Response Criteria for Patients with CNS Tumors**

#### 12.6.1 Measurable Disease

Any lesion that is at minimum 10 mm in one dimension on standard MRI or CT, for CNS tumors.

al Institutes of Health

Institute of the Natio

THIS PROTOCOL IS FOR RESEARCH PURPOSES ONLY, SEE PAGE 1 FOR USAGE POLICY

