- f. Interleukins, Interferons and Cytokines (other than Hematopoietic Growth Factors): ≥ 21 days must have elapsed since the completion of interleukins, interferon or cytokines (other than Hematopoietic Growth Factors).
- g. Stem cell Infusions (with or without TBI):
  - Allogeneic (non-autologous) bone marrow or stem cell transplant, or any stem cell infusion including DLI or boost infusion: ≥ 84 days must have elapsed after infusion, and no evidence of GVHD.
  - Autologous stem cell infusion including boost infusion: ≥42 days must have elapsed after completion.
- h. Cellular Therapy:  $\geq$  42 days must have elapsed since the completion of any type of cellular therapy (e.g. modified T cells, NK cells, dendritic cells, etc.).
- i. XRT/External Beam Irradiation including Protons:  $\geq 14$  days must have elapsed after local XRT;  $\geq 150$  days after TBI, craniospinal XRT or if radiation to  $\geq 50\%$  of the pelvis;  $\geq 42$  days if other substantial BM radiation.
- j. Radiopharmaceutical therapy (e.g., radiolabeled antibody, I-MIBG):  $\geq$  42 days must have elapsed since systemically administered radiopharmaceutical therapy.
- k. Patients must not have received prior exposure to LY2606368.

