#### 4.2 **Exclusion Criteria**

4.2.1 Pregnancy or Breast-Feeding

Pregnant or breast-feeding women will not be entered on this study because there is yet no available information regarding human fetal or teratogenic toxicities. Pregnancy tests must be obtained in girls who are post-menarchal. Males or females of reproductive potential may not participate unless they have agreed to use an effective contraceptive method both during and for 3 months after participation in this study. Abstinence is an acceptable method of contraception.

- 4.2.2 Concomitant Medications
  - 4.2.2.1 Corticosteroids: Patients receiving corticosteroids must have been on a stable or decreasing dose of corticosteroid for at least 7 days prior to enrollment. If used to modify **immune adverse events** related to prior therapy,  $\geq 14$  days must have elapsed since last dose of corticosteroid (See Section 4.1.6.1.d).
  - 4.2.2.2 Investigational Drugs: Patients who are currently receiving another investigational drug are not eligible.
  - 4.2.2.3 Anti-cancer Agents: Patients who are currently receiving other anti-cancer agents are not eligible.
  - 4.2.2.4 Anti-GVHD agents post-transplant: Patients who are receiving cyclosporine, tacrolimus or other agents to prevent graft-versus-host

disease post bone marrow transplant are not eligible for this trial.

- 4.2.2.5 Strong CYP1A2 Inhibitors: Patients must not have received strong CYP1A2 inhibitors (ciprofloxacin, fluvoxamine, zafirlukast) for at least 7 days prior to enrollment and must not receive them for the duration of the study.
- 4.2.2.6 Infection: Patients who have an uncontrolled infection are not eligible.
- 4.2.2.7 Patients who have received a prior solid organ transplantation are not eligible.
- 4.2.2.8 Patients with a history of allergic reactions attributed to compounds of similar chemical or biologic composition to LY2606368 or to its formulation are not eligible.
- 4.2.2.9 Patients who in the opinion of the investigator may not be able to comply with the safety monitoring requirements of the study are not eligible.

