# 12.4 Response Criteria for Neuroblastoma Patients with MIBG Positive Lesions

12.4.1 MIBG Positive Lesions

Patients who have a positive MIBG scan at the start of therapy will be evaluable for MIBG response. The use of I for MIBG imaging is recommended for all scans. If the patient has only one MIBG positive lesion and that lesion was radiated, a biopsy must be done at least 28 days after radiation was completed and must show viable neuroblastoma.

12.4.2 The following criteria will be used to report MIBG response by the treating institution:

Complete response:Complete resolution of all MIBG positive lesionsPartial Response:Resolution of at least one MIBG positive lesion, with
persistence of other MIBG positive lesionsStable disease:No change in MIBG scan in number of positive lesionsProgressive disease:Development of new MIBG positive lesions

- 12.4.3 The response of MIBG lesions will be assessed on central review using the Curie scale14 as outlined below. Central review responses will be used to assess efficacy for study endpoint. See Section 8.2 for details on transferring images to the Imaging Research Center.
  - NOTE: This scoring should also be done by the treating institution for end of course response assessments.

The body is divided into 9 anatomic sectors for osteomedullary lesions, with a 10th general sector allocated for any extra-osseous lesion visible on MIBG scan. In each region, the lesions are scored as follows. The **absolute extension score** is graded as:

- 0 = no site per segment,
- 1 = 1 site per segment,
- 2 = more than one site per segment,
- 3 = massive involvement (>50% of the segment).

[figure not shown]
The **absolute score** is obtained by adding the score of all the segments. See diagram of sectors below:

[figure not shown]

CHILDREN'S Pediatric Early Phase Clinical Trials Networl NCI ONCOLOGY

GROUP

A program funded by the National Cancer nstitute of the National Institutes of Health

The relative score is calculated by dividing the absolute score at each time point by the corresponding pre-treatment absolute score. The relative score of each patient is calculated at each response assessment compared to baseline and classified as below:

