# 12.6.3 Selection of Target and Non-Target Lesions

For most CNS tumors, only one lesion/mass is present and therefore is considered a "target" for measurement/follow up to assess for tumor progression/response. If multiple measurable lesions are present, up to 5 should be selected as "target" lesions. Target lesions should be selected on the basis of size and suitability for accurate repeated measurements. All other lesions will be followed as non-target lesions. The lower size limit of the target lesion(s) should be at least twice the thickness of the slices showing the tumor to decrease the partial volume effect (e.g., 8 mm lesion for a 4 mm slice).

Any change in size of non-target lesions should be noted, though does not need to be measured.

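### The CNS response rules omit the plan's own condition on irradiated lesions and do not track corticosteroid increases, so confirmed shrinkage from either can be counted as antitumor activity

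*Combined protocol and SAP*

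**What the plan says.** All references are to the combined protocol and SAP.

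- **CNS measurability (12.6.1):** "Any lesion that is at minimum 10 mm in one dimension on standard MRI or CT, for CNS tumors".
- **CNS target choice (12.6.3):** "Target lesions should be selected on the basis of size and suitability for accurate repeated measurements". The same section notes that most CNS tumors present as one mass, which is then the target.
- **Other solid tumors (12.2.2.1):** "Tumor lesions that are situated in a previously irradiated area must show definitive evidence of progression to be considered measurable".
- **MIBG-positive neuroblastoma (12.4.1):** where the only positive lesion has been irradiated, "a biopsy must be done at least 28 days after radiation was completed and must show viable neuroblastoma".
- **Washout (4.1.6.1, item i):** at least 14 "days must have elapsed after local XRT". Craniospinal radiotherapy requires 150 days.
- **Steroids (4.2.2.1):** "Patients receiving corticosteroids must have been on a stable or decreasing dose of corticosteroid for at least 7 days prior to enrollment".
- **CNS response calls (12.6.4 and 12.6.7):** PR is a fall of at least 50% in the sum of products from baseline. The overall call uses target lesions, non-target lesions, markers and new lesions.
- **Eligibility (4.1.3):** patients need measurable or evaluable disease, and the reader is sent to 12.2 and 12.3 for the definitions, not to 12.6.
- **Use of the data (1.2.1 and 11.5):** antitumor activity is a secondary aim, and response is reported descriptively.

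**The concern.** The plan recognizes in two of its response sections that prior radiotherapy can make a lesion unsuitable for judging the drug, and sets a condition each time. The CNS section sets none, although CNS tumors are expressly eligible and a single lesion often decides the call. In a single-arm trial no control group separates a late radiation effect, or the effect of more steroid, from the effect of LY2606368.

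What is at stake is how the CR and PR count among CNS patients is read. A signal of activity in CNS tumors, even a descriptive one, could influence what is studied next.

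**Working it through.** The plan states no figure on this point, so there is none to reproduce. The check compares the sections and works out dates from the plan's own windows.

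**1. Sections side by side**

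| Disease group | Condition on an irradiated lesion | Steroid dose used in response call |
|---|---|---|
| Solid tumors (12.2) | Definitive progression required | No |
| Sole MIBG-positive lesion (12.4) | Biopsy showing viable tumor, at least 28 days after radiation | No |
| CNS tumors (12.6) | None | No |

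The radiation gap is an inconsistency between sections. The steroid gap is an omission common to all of them.

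**2. Radiotherapy timing**

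Inputs: local radiotherapy ends at least 14 days before enrollment (4.1.6.1); the projected start is at most 5 days after enrollment (3.9); baseline imaging falls within 14 days before start (4.0); cycles last 28 days (5.1); disease is evaluated at the end of Cycle 1, with a confirmatory scan on the next cycle after a response (8.1, 12.2). Take day 0 as the start of therapy and the shortest permitted washout.

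| | Start on day of enrollment | Start 5 days later |
|---|---|---|
| Radiotherapy ends | day −14 | −(14 + 5) = day −19 |
| Baseline scan, days after radiotherapy | 0 to 14 | 5 to 19 |
| End-of-Cycle-1 scan, days after radiotherapy | 28 + 14 = 42 | 28 + 19 = 47 |
| Next-cycle confirmatory scan, days after radiotherapy | 56 + 14 = 70 | 56 + 19 = 75 |

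The baseline scan can thus fall within 0 to 19 days of radiotherapy. A radiation effect that develops by 42 to 47 days and persists to 70 to 75 days would meet both the PR threshold and confirmation.

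**3. Steroid timing**

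The 7-day rule counts back from enrollment, while the imaging window counts back from start. The last permitted increase before entry is on day −7 (no lag) or day −12 (5-day lag), and the baseline scan can be on day −14. The scan can therefore precede a permitted increase by 14 − 7 = 7 days or 14 − 12 = 2 days. After enrollment, no dose rule applies and 12.6 takes no account of a change.

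**4. Size of one misattributed response**

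Change in response rate = 1/n. The values 6 and 12 are illustrative CNS denominators. The value 30 is the 24 expected evaluable patients plus the 6 additional patients in Section 11.1, assuming all are evaluable for response.

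- n = 6: 16.7 percentage points
- n = 12: 8.3
- n = 30: 3.3

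**The case against.** Several counterarguments have force.

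- **The pointer in 4.1.3.** Section 4.1.2 counts CNS tumors among solid tumors, and 4.1.3 sends the reader to 12.2, so the irradiated-lesion note might be said to reach CNS patients. That works for eligibility at most. CNS response has its own definition in 12.6.1, and the two have to be reconciled.
- **Recurrent or refractory disease is required (4.1.2).** This makes the scenario less common. It is a condition on the patient, however, and does not require that the irradiated target progressed after its radiotherapy.
- **Confirmation and central review.** A reader might infer that one smaller scan is enough for a PR. It is not: Section 12.7 requires confirmation, and Table 3 leaves an unconfirmed response unclassified. Responders are also centrally reviewed (8.2). These steps remove transient or misread shrinkage, but neither has a rule for separating drug effect from radiation or steroid effect.
- **Washout length.** A reader might infer that any CNS irradiation is acceptable two weeks later. The 14 days apply to local radiotherapy only.
- **Steroids.** A reader might infer that the plan ignores them. It does not, since 4.2.2.1 controls the dose before entry. It is also true that no response section uses steroid dose and that the documents nowhere say how much steroids shrink a CNS lesion. This half rests on the general premise that they can, which supports recording and flagging rather than automatic reclassification. Whether doses are already captured cannot be judged, because the CRF packet is separate.
- **False progression.** A reader might extend the point to enlargement from treatment effect being called PD. The documents offer no basis for sizing that, and PD governs removal from therapy, so it is not pressed here.

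**Conclusion.** The concern holds in a limited form. As written, Section 12.6 lets a CNS lesion that received local radiotherapy as little as 14 days before enrollment serve as the sole target without evidence of progression since, and the CNS response call disregards steroid increases after enrollment. Confirmed shrinkage from either cause can enter the CR/PR count for aim 1.2.1.

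The consequence is confined to a descriptive secondary analysis; MTD, DLT assessment and sample size do not depend on it. The documents give neither the number of CNS patients nor how many would be recently irradiated or given more steroid, and the plan defines no CNS stratum or efficacy threshold. A reader might infer a bias of a definite number of percentage points in a CNS response rate. The plan does not support that: the figures above show only what one such response would do under assumed denominators, and the effect is nil if no such patient responds. This is a worthwhile, inexpensive improvement and not a flaw in the main design.

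**What to change.** 1. **Irradiated lesions.** Reconcile 4.1.3, 12.2.2.1 and 12.6.1 with a sentence in 12.6: for counting objective response only, CR or PR in a previously irradiated CNS lesion counts only if that lesion had shown definitive progression after its radiotherapy and before baseline. Otherwise the patient is reported as not evaluable for objective response. State that eligibility under 4.1.3 and the PD and removal-from-therapy rules are unchanged.

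2. **Steroids.** Record the corticosteroid dose at the baseline scan and at each CNS response scan. Report separately any CR or PR obtained on a dose higher than at the baseline scan, and give the CNS response count with and without those cases.

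The change should stay at the level of counting. Copying the 12.2.2.1 note into 12.6.1 unaltered would leave a sole lesion of 10 mm or more neither measurable nor evaluable, because 12.6.2 reserves the evaluable category for disease with no accurately measurable lesion. The table in 12.6.7 would have no row for such a patient, and following the lesion as non-target would change the PD rule. Relabeling a response on a raised steroid dose as SD would contradict the SD definition in 12.6.4. Flagging it avoids this.

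Cost: one extra data field, and an occasional CNS patient who is not evaluable for objective response or whose response carries a flag.
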